13.1 Overview

Analysis of study data will be conducted to address all study objectives and to understand other interrelationships among all data elements of interest to the investigators and of relevance to the objectives of the study. Although the study has recruited 37 practice sites prior to protocol initiation, the analytical plan is based on 30 practice sites as a conservative estimate due to potential attrition.

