13.6 Statistical Hypotheses

Primary hypotheses: In each of the high-risk and low-risk strata, the primary endpoint analysis performs a test of superiority to assess whether the proportion of infants whose pediatric clinician is adherent to PPA Guidelines is different in the intervention arm compared to the control arm. A multiplicity adjustment will not be applied to the primary analysis because high and low-risk children represent independent risk strata where pediatric clinicians must take different steps to achieve adherence.

Null hypothesis: $P(\text{intervention group}) = P(\text{control group})$ where P denotes the proportion adherent.

Alternative hypothesis: $P(\text{intervention group}) \neq P(\text{control group})$

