13.7 Sample Size Considerations

Power has been computed for primary and exploratory binary adherence outcomes and secondary peanut allergy outcomes. In order to compute power, six quantities have been specified: the type 1 error rate, the number of practice sites, the number of patients expected per practice site, the within cluster correlation, the average proportion adherent (or peanut allergic) over all practice sites and intervention arms, and the difference in proportion adherent (or peanut allergic) between the intervention and control arms. Calculations assume a type 1 error of 0.05. In this study, investigators can control the number of practice sites invited to participate in the study but cannot control the number of infants assessed at each practice site. Since deployment of the intervention and data collection are through the EHR, inclusion of additional practice sites does not require significant additional budget. Therefore, the choice of number of practice sites is based primarily on the number expected to participate and not on budgetary or statistical power concerns. We estimate that at minimum 30 clinics will participate. Using a preliminary EHR data pull, we estimate being able to assess on average 17 high-risk and 333 low-risk per clinic in 18 months for a total sample size of approximately 500 high-risk and 10,000 low-risk infants.

Since investigators cannot control the number of infants assessed, power calculations describe the differences between intervention arms in study outcomes that are detectable with 80% power for our given study sample sizes, rather than the sample sizes needed to be able to detect given differences between intervention arms in study outcomes.

Statistical power for primary and exploratory adherence outcomes: We assume a within cluster correlation of 0.07 for the pediatric clinician adherence outcomes, estimated from a preliminary EHR data pull. Similar studies have assumed lower correlations in the range of 0.001-0.01^{39,40} however, so we expect this estimate to be conservative. To further be conservative, we assume the average proportion adherent over all practice sites and intervention to be 0.50. These and the previously described assumptions and sample sizes allow us to detect with >80% power an absolute difference in proportions of adherence of $\geq 18\%$ in high-risk infants and $\geq 14\%$ in low-risk infants.

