Statistical power for secondary peanut allergy outcome: We assume a within cluster correlation of 0.02 for the peanut allergy outcome, estimated from a preliminary EHR data pull on general food allergy. Peanut allergy prevalence data referenced earlier in this document provide estimates of the incidence of peanut allergy at age 2 of 13.8% for high-risk infants and 1.5% in low-risk infants. In high-risk infants, these and the previously described assumptions and sample sizes allow us to detect with >80% power an absolute difference in proportions with peanut allergy of 8.2% in high-risk infants (intervention and control arm proportions 5.4% and 13.8%). In low-risk infants, we can detect an absolute difference in proportions with peanut allergy of 0.98% (intervention and control arm proportions 0.11% and 1.50%). In high-risk infants, the LEAP study showed a 14% absolute difference in proportions with peanut allergy contrasting early introduction of peanut to avoidance. Compared to this, we are powered to detect smaller reductions in peanut allergy that might be expected with a CDS intervention.

14. Identification and Access to Source Data, Monitoring Plan

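### The low-risk detectable peanut-allergy difference is given as 0.98 points beside arm proportions that differ by 1.39; the design has about 43% power at 0.98, not 80%.

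*Combined protocol and SAP*

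**What the plan says.** Section 13.7 explains that infant numbers cannot be controlled, so its calculations give "differences between intervention arms in study outcomes that are detectable with 80% power for our given study sample sizes". The shared inputs are 30 clinics, on average 17 high-risk and 333 low-risk infants per clinic, and a type 1 error of 0.05. Section 13.1 confirms that "the analytical plan is based on 30 practice sites as a conservative estimate due to potential attrition".

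For peanut allergy the section takes a within-cluster correlation of 0.02 and incidences of 13.8% (high risk) and 1.5% (low risk). It then gives two detectable differences:

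- High risk, with power above 80%: "8.2% in high-risk infants (intervention and control arm proportions 5.4% and 13.8"%.
- Low risk: "In low-risk infants, we can detect an absolute difference in proportions with peanut allergy of 0.98% (intervention and control arm proportions 0.11% and 1.50"%.

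The paragraph ends by citing a 14-point difference from the LEAP study in high-risk infants and concluding: "Compared to this, we are powered to detect smaller reductions in peanut allergy that might be expected with a CDS intervention".

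**The concern.** The low-risk sentence gives two different answers to one question. The stated difference is 0.98 points, while the two arm proportions differ by 1.39. They cannot both be the difference detectable with 80% power.

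The two figures describe very different claims. A fall of 0.98 from 1.50 is a 65% relative reduction. A fall to 0.11 is a 93% reduction, so peanut allergy would almost have to disappear from the intervention arm. A reader who takes the stated difference will think the low-risk comparison much more sensitive than it is, and may later read a null result as evidence against a 65% reduction. Low-risk infants are about 10,000 of the 10,500 expected, and their peanut-allergy incidence is a named secondary endpoint.

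**Working it through.** **Inputs.** From 13.7: type 1 error 0.05, target power 80%, 30 practices, 333 low-risk and 17 high-risk infants per practice, correlation 0.02 for peanut allergy and 0.07 for adherence, low-risk incidence 1.5%. From the end of 13.2: 1:1 allocation, so 15 practices per arm. The test is taken as two-sided because 13.6 writes the primary alternative that way; no alternative is written for the secondary endpoint. No allowance is made for missing outcomes, since 13.7 gives none.

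**Formulas.** Design effect DE = 1 + (m − 1) × ICC. Effective n per arm = 15 × m / DE. SE = √[p₁(1 − p₁)/n + p₂(1 − p₂)/n]. Power = Φ(difference/SE − 1.96).

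**Subtraction.** 1.50 − 0.11 = 1.39, not 0.98.

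**Does the method reproduce the plan's other figures?** With the pooled-variance form of the same calculation:

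| Comparison in 13.7 | DE | Power |
|---|---|---|
| High-risk adherence, 18 points around 50% | 1 + 16 × 0.07 = 2.12 | 80.1% |
| Low-risk adherence, 14 points around 50% | 1 + 332 × 0.07 = 24.24 | 81.4% |
| High-risk allergy, 5.4% vs 13.8% | 1 + 16 × 0.02 = 1.32 | 80.3% |

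It does, so this is a fair yardstick for the low-risk allergy figure.

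**Low-risk allergy, 30 practices.** DE = 1 + 332 × 0.02 = 7.64. Effective n per arm = 15 × 333 / 7.64 = 653.8.

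- Printed pair, 0.11% vs 1.50%: SE = 0.493 points; 1.39/0.493 = 2.82; power 0.805 (pooled 0.804).
- Stated difference, 0.52% vs 1.50%: SE = 0.552 points; 0.98/0.552 = 1.77; power 0.426 (pooled 0.425).

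**Other methods.** The normal approximation is rough here: 0.11% of 15 × 333 = 4,995 intervention infants is about 5.5 expected cases. Two further methods were therefore run: a t reference (27 df for 30 practices, 34 df for 37 practices split 18 and 19), and a simulation with a practice-level t-test. The simulation assumes beta-binomial variation between practices with correlation 0.02.

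| | Normal | t reference | Simulation |
|---|---|---|---|
| Power at 0.98, 30 practices | 0.43 | 0.40 | 0.46 |
| Power at 0.98, 37 practices | 0.50 | 0.48 | 0.55 |
| Power at 1.39, 30 practices | 0.805 | 0.776 | 0.91 |
| 80% detectable difference, 30 practices (points) | 1.38 | 1.42 | about 1.28 |
| 80% detectable difference, 37 practices (points) | 1.29 | 1.32 | about 1.20 |

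**Can 0.98 be rescued?** Measuring it from the intervention figure (0.11% vs 1.09%) gives 63% power. Centring it on an average of 1.5% (1.01% vs 1.99%) gives 31%. A one-sided test at 0.05, with control at 1.50%, gives 55%. Reaching 80% at 0.52% vs 1.50% would take about 38 practices per arm (76 in all), or a correlation of about 0.006 instead of 0.02.

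**High-risk sentence.** 13.8 − 5.4 = 8.4, but 8.2 is stated. Effective n per arm = 15 × 17 / 1.32 = 193.2.

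| Difference, 30 practices | Unpooled | Pooled | t reference, 27 df |
|---|---|---|---|
| 8.2 points | 0.785 | 0.779 | 0.755 |
| 8.4 points | 0.808 | 0.803 | 0.779 |

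With 37 practices, power at 8.2 is 0.86.

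**The case against.** The near-elimination figure is not hidden: the arm proportions stand in the same sentence, so the text is contradictory rather than uniformly too favourable. The low-risk sentence also does not repeat a power level. Both points are fair, but 80% is set for all these calculations earlier in 13.7, and the difference is the figure a reader is most likely to carry away.

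The documents do not name the power method, so it is an inference that 0.98, rather than the pair, is the wrong figure. It could be left over from a run with a correlation near 0.006. That cannot be excluded, but the plan states 0.02, and under the stated inputs the pair gives 80% while no reading of 0.98 that was tried does.

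A third objection is that the power attached to 1.39 depends on the method (0.78 to 0.91 above). This stands, and is why the correction should name the method as well as the number.

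Finally, the closing LEAP comparison is introduced as a high-risk result and holds there, since 8.2 and 8.4 are both below 14. Its last sentence follows the low-risk figure without repeating that limit, but adding it is an optional clarification. It is also true that 13.7 did not choose the number of practices on power grounds, so no design decision rests on the 0.98.

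**Conclusion.** The concern holds. The stated low-risk difference of 0.98 points disagrees with its own arm proportions and with the design. Under the plan's inputs, power at 0.98 from a 1.50% control rate is 0.40 to 0.46 with 30 practices and 0.48 to 0.55 with 37. The 80% detectable difference with 30 practices is 1.28 to 1.42 points depending on method, and the printed pair (1.39) matches the normal approximation.

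These results rest on a two-sided 0.05 test, equal practice sizes, a correlation of 0.02, a control incidence of 1.5% and complete outcomes. The high-risk mismatch (8.2 against 8.4) moves power by about two percentage points and is minor. The error should be corrected, but it concerns a secondary-endpoint power statement only: the primary power figures, the tests and the sample size stand.

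**What to change.** In 13.7:

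1. Replace 0.98% with 1.39% (0.11% against 1.50%, about a 93% relative reduction), after checking it against the sponsor's own calculation output. State the power at that difference: 80% under the normal approximation.
2. Replace 8.2% with 8.4% (5.4% against 13.8%).
3. Name the power method, because the answer is sensitive to it at about 5.5 expected intervention-arm cases.
4. Add one sentence saying that the low-risk comparison has 80% power only for a near-elimination of peanut allergy. Optionally, limit the closing comparison with LEAP explicitly to high-risk infants.

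The cost is a wording change in one section. The low-risk detectable difference will look less favourable than it does now; nothing else in the design or analysis changes.

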14.1. Source Data

Source documents and source data are considered to be the original documentation where subject information, visits consultations, examinations and other information are recorded. Documentation of source data is necessary for the reconstruction, evaluation and validation of clinical findings, observations and other activities during a clinical trial. In this trial, the following source documents will be present:

- Paper source documents will be created when a study coordinator obtains an informed consent form, generates a log that links the child participants to a practice, pediatric clinician and caregivers, and links all participants to a unique study identification number.
- Electronic health records data

The completion of each online survey will create source electronic data on the survey vendor's

14.2. Access to Source Data

The site investigators and site staff will make all source data available to the DAIT/NIAID, as well as to relevant health authorities. Authorized representatives as noted above are bound to maintain the strict confidentiality of medical and research information that may be linked to identified individuals.

14.3. Monitoring Plan for Consent Process

A copy of the caregiver survey information sheet will be provided to the participant and stored in the study records on a secure system. Every month, study staff will review study records to ensure that consent was obtained and documented. In the event of a failed consent documentation we will immediately pause study activity for the participant in question and document the protocol deviation and report it to the appropriate parties.

No monitoring is necessary for clinician survey consent forms as consent is implicit upon survey completion.

15. Quality Assurance and Quality Control

Data collection will take place at both the practice network (e.g., Lurie Community Connect, Peoria area, Alliance Chicago) and practice level. Each clinical site will perform internal quality management of study conduct, data collection, documentation and completion. An individualized quality management plan will be developed to describe each site's quality management processes. Each practice network PI will be responsible for organizing data collection at the practice level.

Data from participating practices' EHRs will be extracted through an automated process established by the DCC and sent via a secure file transfer protocol (SFTP). Practices will be provided a data dictionary to identify the appropriate elements and visits/services to extract. The DCC will develop Extract Transform Load (ETL) scripts on behalf of each practice network (with the appropriate approvals from the practices). The ETL scripts will be run on a regular basis so the DCC data manager will have a complete EHR-based data file for reporting compliance and participation metrics.

The DCC data manager will supervise data collection progress, consent and study enrollment, survey completion, identify potential data quality issues, alert study leadership and appropriate staff members to resolve any issues and will assure overall integrity of the data used for analysis. The DCC data manager will work with each practice network through the network PI and Informatics team to assure adherence to the study protocol and to implement quality control (QC) procedures. Data QC checks will be generated from the EHR database on a weekly basis.

The practice networks will provide direct access to all trial related sites, source data/documents, and reports for the purpose of monitoring and auditing by the sponsor, and inspection by local and regulatory authorities.

16. Protocol Deviations

16.1. Protocol Deviation Definitions

Protocol Deviation: The investigators and site staff will conduct the study in accordance to the protocol; no deviations from the protocol are permitted. Any change, divergence, or departure from the study design or procedures constitutes a protocol deviation. As a result of any deviation, corrective actions will be developed by the site and implemented promptly.

Major Protocol Deviation (Protocol Violation): A Protocol Violation is a deviation from the IRB approved protocol that may affect the subject's rights, safety, or well-being and/or the completeness, accuracy and reliability of the study data. In addition, protocol violations include willful or knowing breaches of human subject protection regulations, or policies, any action that is inconsistent with the NIH Human Research Protection Program's research, medical, and ethical principles, and a serious or continuing noncompliance with federal, state, local or institutional human subject protection regulations, policies, or procedures.

Non-Major Protocol Deviation: A non-major protocol deviation is any change, divergence, or departure from the study design or procedures of a research protocol that does not have a major impact on the subject's rights, safety or well-being, or the completeness, accuracy and reliability of the study data.

16.2. Reporting and Managing Protocol Deviations

The study site principal investigator has the responsibility to identify, document and report protocol deviations as directed by the study Sponsor. However, protocol deviations may also be identified during site monitoring visits or during other forms of study conduct review.

Upon determination that a protocol deviation has occurred, the study staff will a) notify the site Principal Investigator, b) notify the study data center, and c) will complete a Protocol Deviation form. The Protocol Chair will document all protocol deviations in the Trial Master File and promptly report the deviations to the DAIT/NIAID Medical Monitor and Project Manager. The DAIT/NIAID Medical Monitor and Project Manager will make the decision as to whether the Deviation is major or not and what the impact of the Deviation on the study participant or the entire study may be, and will review and approve the action plan that will be implemented as a result of the Protocol Deviation.

17. Ethical Considerations and Compliance with Good Clinical Practice

17.1. Statement of Compliance

This clinical study will be conducted using good clinical practice (GCP), as delineated in *Guidance for Industry: E6 Good Clinical Practice Consolidated Guidance*, and according to the criteria specified in this study protocol. Before study initiation, the protocol and the informed consent documents will be reviewed and approved by the IRB. Any amendments to the protocol or to the consent materials will also be approved by the IRB before they are implemented.

17.2. Informed Consent Process

Caregiver Survey Consent

The informed consent process for caregiver survey participation will occur via phone or in-person to provide information about the study to a prospective participant and allow adequate time for review and discussion prior to his/her decision. The method of consent will be at the discretion of the prospective participant. During both the phone and in-person consent process, research study staff will review the consent with the prospective

participant in the preferred language and answer any questions. The prospective participant will be told that being in the trial is voluntary and that he or she may withdraw from their part at any time, for any reason. Consent materials will be presented to participants in English or Spanish. A copy of the information sheet will be provided to the participant.

The consent process will be ongoing. The information sheet will be revised when important new safety information is available, the protocol is amended, and/or new information becomes available that may affect participation in the study.

Pediatric Clinician Survey Consent

The pediatric clinician will only receive an online information sheet to complete the consent process. They will directly receive an email with the online survey invitation link and a statement of consent. The invitation will state: "Your participation in this survey is voluntary. Your individual answers will remain confidential and reported only in the aggregate." Consent of the invited respondent to participate will be implied when the participant opens the survey URL in their web browser and/or answers at least one question in the survey. While taking the survey, a participant may end the survey at any time by not answering any further questions. Once a participant provides any survey data, the data automatically enters the study database.

17.3. Privacy and Confidentiality

Participant (including caregivers, their children, and pediatric clinicians) privacy and confidentiality will be respected throughout the study. Each participant will be assigned a unique identification number and these numbers rather than names will be used to collect, store, and report participant information. Site personnel will not transmit documents containing personal health identifiers (PHI) to the study sponsor or their representatives. Each pediatric clinician and caregiver survey will be coded with a unique identification number and stored on password protected computers and servers. Only aggregated data will be shared. Participant-specific data will not be shared with care providers or colleagues at the practice and no practice personnel will have access to survey responses. To further protect the confidentiality of pediatric clinicians, aggregated data by practice will not be shared.

18. Publication Policy

This trial will comply with the [NIH Public Access Policy](#), which ensures that the public has access to the published results of NIH funded research. It requires scientists to submit final peer-reviewed journal manuscripts that arise from NIH funds to the digital archive [PubMed Central](#) upon acceptance for publication.

References

